The COVID-19 pandemic necessitated a rapid transition nationally from in-person to telemedicine (Augsterfer, Mollica, & Lavelle, 2018; Torous & Wykes, 2020; Kalin, et al., 2020), a change that occurred in our clinic as well. Over the last 2 years, research members of Carilion Clinic Psychiatry and Virginia Tech Psychology departments have been actively using PROM data to assess psychiatric health outcomes before and after the outbreak of COVID-19 in the United States. Initial results indicate that patients who received care via telemedicine not only **did not experience worsening symptoms, but showed improvements in depression, anxiety and psychological functioning**. However, without a control group of untreated patients to compare, the impact of telemedicine plus PROMs remains unclear. A wait-list control group design would allow us to compare patients receiving telemedicine and repeated completion of PROMs (current practice) to patients referred to psychiatry, but not receiving telemedicine treatment or completing PROMs during the same time period. We propose randomizing wait-list individuals to one of two groups to assess the influence of time alone awaiting initial psychiatric clinician assessment (no intervention) versus minimal intervention using repeated PROMs and microlearning patient education videos while awaiting initial psychiatric clinician assessment. This kind of design allows assessment for the influence of time and the type of health service contact that replicates the basics of measurement-based psychiatric services (measurement of symptomology and well-being), but with none of the benefits of psychiatric supports, interventions, and techniques.

10.5 Provide background information about the research question(s.) Explain why the research is needed and include the relevance of this research to the contribution of this field of study.

Please include the current state of knowledge about your project topic by summarizing and synthesizing the available research (including published data) to provide justification for the study. Include a reference list of literature cited to support the protocol statement, either in your response below or as a supplemental document as part of the application packet.

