improvements in depression, anxiety and psychological functioning. However, without a control group of untreated patients to compare, the impact of telemedicine plus PROMs remains unclear. A wait-list control group design would allow us to compare patients receiving telemedicine and repeated completion of PROMs (current practice) to patients referred to psychiatry, but not receiving telemedicine treatment or completing PROMs during the same time period. We propose randomizing wait-list individuals to one of two groups to assess the influence of time alone awaiting initial psychiatric clinician assessment (no intervention) versus minimal intervention using repeated PROMs and reviewing microlearning patient education videos while awaiting initial psychiatric clinician assessment. This kind of design allows assessment for the influence of time and the type of health service contact that replicates the basics of measurement-based psychiatric services (measurement of symptomology and well-being), but with none of the benefits of psychiatric supports, interventions, and techniques.

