10.6 State the research hypothesis or the question that the research will answer.

List the research objectives and expected outcomes. A primary outcome or objective must be identified. After the statement of the primary objective, secondary objectives may be listed. Objectives should be simple and specific.

Aim 1 will use PROMs to assess the symptomology and well-being of adult individuals on a wait-list group referred to CC-P&BM clinic from their initial referral to their initial psychiatric session.

In particular, we propose randomizing wait-list individuals to one of two groups to assess the influence of time alone awaiting initial psychiatric clinician assessment (no intervention) versus minimal intervention using prospective monthly repeated PROMs and viewing microlearning patient education videos while awaiting initial psychiatric clinician assessment.

Aim 2 will use PROMs to determine whether there is a difference in clinical symptomology and well-being for patients during telemedicine treatment with their practitioner compared to wait-list individuals.

10.7 State how qualitative and/or quantitative data will be analyzed in order to answer the research questions.

Include an analysis from a statistician (or someone familiar with statistical methods) that either indicates the power calculation for the sample size necessary to meet the primary study outcome or objective OR a statement from the statistician indicating reasons why a power calculation is waived or not necessary for this study. Also include the statistical test(s) that will be used to analyze your primary study objective (t-test, chi-square, etc.). Secondary outcomes may be listed as descriptive.

If this is a proof of concept or feasibility study that includes limited efficacy testing, please provide a description on how your design will determine if an intervention should be recommended for broader efficacy testing. If a study is meant to be solely descriptive, then the primary outcome or objective must be limited in scope. As such, the study results apply only to the sample being studied, and conclusions cannot be drawn about the larger population.

This is required for ALL studies, as this section helps the IRB confirm the data being collected are relevant to the study aims and planned analysis.

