The primary outcome of interest is the change in total PROM score for each assessment required of patients enrolled in the study. Initial PROM scores will be acquired and assessed after referral into the CC-P&BM program. The potential to receive few records per patient is believed to be relatively high; therefore, the final PROMs completed for each assessment will be used to determine the change in total score. This change will be compared between patients receiving telemedicine and those of the control (wait-list) groups. A two-sample t-test or non-parametric equivalent of the mean change in total PROM will be performed to determine if the change is significantly different among treatment types. An alpha of 0.05 will be used to assess statistical significance. Univariate and multivariate analyses may occur to measure numeric variables by measures of central tendency and variation and categorical variables by frequencies and percentages. Trends of PROM scores will be evaluated between treatment types by the time in program.

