2. Randomly assign patient into group (REDCap will do this when you start a new patient record); inform patient of the group they have been randomly assigned into to provide further instructions.
3. Provide all patients with CONNECT phone number at termination of the call.

Initial consenting process occurs after routine clinical psychiatry intake assessment by intake coordinator (if intake coordinator assesses that patient has capacity to pursue study discussion): 30-45 min consent process through REDCap or hard copy in-person. REDCap will be utilized to perform randomization. There is no blinding due to the nature of the wait-list control groups; both patients and investigators will be aware of study group assignment.

No intervention group randomization: no additional time/study procedures occur after consent; **SO C monthly PROMs DO NOT begin until after initial psychiatric provider evaluation for 6 additional months.**

Minimal intervention randomization: each month PROMs including PHQ-9, GAD-7 and BASE-6 are sent automatically for subject to complete via email or cell phone before initial psychiatric provider appointment - takes approximately 15 minutes to complete; watching microlearning videos about illness/symptoms takes approximately 15-30 minutes to watch depending on # videos recommended. Current wait-time for patients to see MD provider is 3-4 months; therefore, subjects in the minimal intervention group will participate in the study for up to 6 months before beginning regular treatment with provider.

PROM data from both groups will continue at initial psychiatric provider evaluation and monthly as is current clinical practice. Therefore, an additional 6 months of PROM data for each group will be followed to assess the research question of whether a no intervention or minimal intervention group may provide benefits to patients waiting to be seen and followed by psychiatric providers.

Total study participation time = 6-12 months depending on length of wait time before first psychiatric provider appointment

You must attach surveys, instruments, interview questions, focus group questions, etc. in the Initial Submission Packet and label them clearly.

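### Aim 2 sets telemedicine against the wait-list arms undivided and never names telemedicine versus no intervention, the contrast its own rationale calls for

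*Combined protocol and SAP*

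**What the plan says.** Sections 10.4 and 10.5 justify the trial by a missing comparator: "However, without a control group of untreated patients to compare, the impact of telemedicine plus PROMs remains unclear". They describe that comparator as "patients referred to psychiatry, but not receiving telemedicine treatment or completing PROMs during the same time period".

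The trial randomises waiting patients to two arms. In the no-intervention arm, nothing happens between intake and the first clinician appointment (22.2). In the minimal-intervention arm, "each month PROMs including PHQ-9, GAD-7 and BASE-6 are sent automatically for subject to complete" (19.1), and education videos are assigned (10.5, 22.2). Sections 19.1 and 19.3 call both arms wait-list control groups.

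Aim 2 in section 10.6 looks for a "difference in clinical symptomology and well-being for patients during telemedicine treatment with their practitioner compared to wait-list individuals". Section 10.7 then states: "This change will be compared between patients receiving telemedicine and those of the control (wait-list) groups". On the test it says: "A two-sample t-test or non-parametric equivalent of the mean change in total PROM will be performed". On the significance level: "An alpha of 0.05 will be used to assess statistical significance". No arm-specific contrast, three-group test or multiplicity rule is given.

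**The concern.** The comparator in the rationale and the comparator in the analysis do not match. Only the no-intervention arm resembles the untreated, unmeasured patients of 10.4 and 10.5. The analysis sections refer to wait-list individuals or groups without distinguishing the arms, and name a single two-group test. Taken at face value, telemedicine is on one side and both wait-list arms together are on the other.

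The result would then depend on the answer to Aim 1. Any effect of monthly PROMs and videos, good or bad, enters the control mean and changes the apparent effect of telemedicine. The pooled contrast would also answer neither of two clear questions: what telemedicine with PROMs achieves over plain waiting, and what the clinician adds over measurement and education. If two separate tests were intended instead, the plan does not say which one matters most or how the error rate is controlled.

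**Working it through.** **Inputs.** Total enrolment is 200 (11.2) and the no-intervention arm is 100 (11.3). The minimal arm is not listed, so the remaining 100, and hence a split of about 1:1, is inferred. Alpha is 0.05 (10.7); two-sided is assumed. The plan gives no effect size, SD or power, so it has no figure to reproduce. Effects below are assumptions.

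**1. Which arm fits the rationale?**

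| Requirement in 10.4 and 10.5 | No intervention | Minimal intervention |
|---|---|---|
| No telemedicine while waiting | yes | yes |
| No PROMs while waiting | none repeated; intake and first visit only | no, monthly |
| No other intervention | yes | no, assigned videos |

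**2. Shift of a pooled control.** Count improvement as positive. Let the mean change be c with no intervention, c + m with minimal intervention, and c + T with telemedicine.

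- Pooled control = [100c + 100(c + m)] / 200 = c + m/2
- Pooled contrast = (c + T) − (c + m/2) = T − m/2

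For m = 1, 2, 3 PHQ-9 points the shift is 0.5, 1.0, 1.5 points, and telemedicine is understated by that amount. For m = −1 it is overstated by 0.5.

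**3. Carry-over.** Step 2 assumes that the treated change is untouched by the earlier minimal intervention. If the treated group carries an average carry-over k, the pooled contrast is T + k − m/2.

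- Treated patients are a separate concurrent group: k = 0, and step 2 stands.
- Treated patients are the same participants, change is counted from referral, and the gain is fully kept: k = m/2, and the shift cancels.
- Same participants, change counted from the first provider visit, with less room left to improve: k < 0, and the understatement grows.

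The plan does not settle which case applies. The end of 10.5 points to the same participants followed after their wait. Earlier text in 10.4 and 10.5 suggests current-practice patients over the same period. Section 10.7 takes initial scores after referral and the last PROM completed, without giving a baseline for the treated group.

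**4. Power (illustration).** Assume independent groups, SD = 1, T = 0.4, k = 0, and m = fT, so the pooled effect is 0.4(1 − f/2). SE = √(1/n_control + 1/n_tele); power ≈ Φ(effect/SE − 1.96).

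| Control | Effect (SD) | Power, 100 telemedicine | Power, 200 telemedicine |
|---|---|---|---|
| No intervention only (100) | 0.40 | 80.7% | 90.4% |
| Pooled (200), f = 0.25 | 0.35 | 81.5% | 93.8% |
| Pooled (200), f = 0.5 | 0.30 | 68.8% | 85.1% |
| Pooled (200), f = 1 | 0.20 | 37.2% | 51.6% |

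The break-even is f = 2(1 − SE_pooled/SE_single). With 100 telemedicine patients it is 2(1 − √0.015/√0.020) = 0.27; with 200 it is 2(1 − √0.010/√0.015) = 0.37. Below these values pooling gains power, but the quantity estimated differs from T for any f other than 0.

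**5. If two separate tests were meant.** Two unadjusted tests at 0.05 give a family-wise error of up to about 1 − 0.95² = 9.75% (independence approximation).

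**The case against.** The strongest reply is that the plan never says the arms are combined. Section 10.7 uses the plural for the wait-list groups and speaks of treatment types; 10.5 analyses both groups, and 19.1 follows PROM data for each. A two-sample test against each arm in turn is compatible with that wording. This stands: a reader might infer a stated pooling rule, but the documents support it only as the more natural reading. It does not remove the problem, because the separate-tests reading also lacks a named contrast and a multiplicity rule.

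A second reply is that both arms are controls by design: 10.4 and 10.5 present the minimal arm as contact without psychiatric support, so that time and contact can be told apart. That is a sound reason to have two arms. It is also a reason not to merge them.

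Third, a reader might infer that telemedicine is never compared with untreated patients. That is too strong. The no-intervention arm would be about half of a pooled control; what is missing is a separate comparison with it. Nor is that arm free of PROMs, since it completes them at intake and at the first visit.

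Finally, pooling can be the more powerful choice when the minimal intervention does little (step 4). That is true, but whether it does little is what Aim 1 is meant to find out.

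**Conclusion.** The plan should be changed. Sections 10.6 and 10.7 do not name telemedicine versus no intervention, the contrast closest to the comparator that 10.4 and 10.5 require. On their natural reading they dilute it with an arm given monthly PROMs and videos. Under 1:1 pooling the control mean shifts by half of the minimal-intervention effect: 0.5 to 1.5 PHQ-9 points for assumed effects of 1 to 3. This rests on the inferred split, on pooling being what is meant, and on a treated change unaltered by the earlier minimal intervention.

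Two stronger conclusions are tempting and not supported. One is that telemedicine must be understated because Aim 1 expects a benefit. Aim 1 states no direction, and 13.7 and 23.1 recognise that completing the measures could worsen how patients feel, so the shift can go either way. The other is that carry-over into treatment adds to the understatement. Its direction cannot be determined, because the source and baseline of the treated group are not stated.

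**What to change.** In 10.6 and 10.7:

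- Name telemedicine versus the no-intervention arm as the main Aim 2 contrast.
- Make telemedicine versus the minimal-intervention arm a separate secondary contrast, read as what clinician care adds over PROMs and videos.
- State that the wait-list arms are not pooled.
- State the multiplicity rule, for example testing the secondary contrast only after the main one succeeds.
- Report telemedicine-phase change by randomised arm. This is needed as well as the new control: if the same participants supply both sides and a waiting-period gain is counted in the treated change, a no-intervention control alone leaves k = m/2 on the treated side.

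This is a change of wording only, since the randomised group is already held in REDCap (9.15). The cost is precision. With about 100 rather than about 200 controls, the difference detectable with 80% power rises from 0.343 to 0.396 SD with 100 telemedicine patients, or from 0.280 to 0.343 SD with 200, under the assumptions of the power illustration. The smaller figures apply to the diluted contrast.

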CC-P&BM currently has a wait-list of over 300 adults referred for mental health evaluation and treatment. Access to psychiatric clinicians remains insufficient despite increasing numbers of providers in our clinic and the mental health needs associated with the pandemic are rising. As a result, a clinical intake coordinator (Licensed Professional Counselor) began in the CC-P&BM ambulatory clinic September 2021. This coordinator will individually contact people on the wait-list for psychiatric care by phone as part of routine care, beginning with the referrals most remote in time. The coordinator will complete an intake assessment for each wait-list individual who wants a psychiatric referral. Prior to the initial intake assessment by the intake coordinator, wait-list individuals will receive a bundle of PROMs automatically (through Owl Insights) to complete. These measures include the PHQ-9, GAD-7, BASE-6, DAST-10, USAUDIT, Covid Event Checklist and the Adult Behavioral Health Screen (ABHS), all of which are currently used in routine ambulatory care. The intake coordinator will complete the intake assessment, noting the completion, and scores of, the PROMs. Scores of the PHQ-9, GAD-7 and BASE-6 will be utilized to triage the most severe referrals and move them up for a sooner appointment (the triage system of scores and Nurse-Practitioner vs Medical Doctor screening questions are attached to this application). Any concern about patient safety is also addressed immediately during this intake and is also noted in the materials attached to this application. **Up to this point, all intake coordinator/referral interaction are part of routine care.**

If eligible and capable of consent based on intake coordinator clinical judgement, individuals will then be randomized to participate to the no intervention group (completion of screening PROMs only during the intake coordinator assessment) or the minimal intervention group (intake coordinator assessment, including PROM screening and then prospective monthly PROM completion in addition to assigned microlearning

patient education videos). We will analyze changes in PROM scores for individuals engaged in both wait-list groups and compare results to their PROM scores at the initial provider telemedicine visit and over time (6 months post first provider assessment). Consent may be in-person with hard copy consent forms and signatures or through e-Consent either in-person using ipads or remotely using REDCap.

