Provide a study schedule and list all activities or procedures that will be performed and describe the frequency and duration of research procedures, diagnostic and research tests, questionnaires or surveys, specimen collection, and experiments, including screening, intervention, follow-up etc in step-by-step chronological order. State the length of time subjects will be in the study and the expected amount of time required for each study visit or activity. Describe how, when and where research activities will be administered and analyzed. If the research includes blinding, indicate whether researchers or subjects will be "unblinded" to study assignment and describe when and how this will be done.

See Triage Program Working Details attached to this application for detailed description. Each survey is also included as attachments to this application.

Steps include:

The study will be introduced after the patient has completed the intake. At the end of the intake /assessment, the intake coordinator (team member) will describe the study to the potential participant and participant is able to confirm understanding about the study using the questions detailed in section 12.7. Consent is obtained either remotely or in-person, and a copy will be given to the patient in-person or emailed/mailed if remote. Introduction of the study will be, "We are researching if these measurements are helpful to people waiting for a psychiatric evaluation. Participation in the research is voluntary and you will be assigned randomly to either wait until your first appointment with your provider to complete these measurements again or complete these measurements every month until your first appointment with your provider." (The three measures they complete each month are the PHQ-9 depression, GAD-7 anxiety, and BASE-6 daily functioning). "Participation in this study is not linked to your psychiatric care – that is, it won't affect the wait-time to getting your initial appointment with your provider either way. Are you interested in participating in this study?"

1. If patient says yes, proceed to REDCap and complete consent process – you will need to set up a new participant record in RedCap and enter demographic information.
 1. Depending on which group the patient is assigned you will need to change the OWL Insights to not automatically send the inventories monthly if they are only in the 1x at onset group (no intervention).

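### Section 10.7 tests telemedicine against wait-list with a two-sample test without saying who the telemedicine patients are; if they are the enrolled participants after their first visit, as best supported, the standard error is wrong.

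*Combined protocol and SAP*

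**What the plan says.** Section 10.7 of the combined protocol and SAP sets the contrast: "This change will be compared between patients receiving telemedicine and those of the control (wait-list) groups". The test is "A two-sample t-test or non-parametric equivalent of the mean change in total PROM will be performed", and "An alpha of 0.05 will be used to assess statistical significance". On forming the change, it says that "the final PROMs completed for each assessment will be used to determine the change in total score", with initial scores taken after referral. No paired, repeated-measures or mixed model is named. The section adds only that score trends will be looked at by time in the programme.

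Other sections bear on who supplies the telemedicine scores:

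- **10.5, last paragraph of the background.** Changes in both wait-list groups will be analysed, and the team will "compare results to their PROM scores at the initial provider telemedicine visit and over time (6 months post first provider assessment").
- **19.1.** "PROM data from both groups will continue at initial psychiatric provider evaluation and monthly as is current clinical practice", for a further 6 months in each group. Section 19.4 repeats this.
- **19.1, introductory script.** A no-intervention participant will "wait until your first appointment with your provider to complete these measurements again".
- **9.15.** The only group variable listed for the data manager's view of REDCap is the randomised wait-list group.
- **11.2 and 11.3.** The total is 200 subjects. The only cohort size given is 100 for the no-intervention wait-list group.
- **10.4 and 10.5, rationale.** The design is said to "compare patients receiving telemedicine and repeated completion of PROMs (current practice) to patients referred to psychiatry" who are untreated over the same period, which reads as different people.
- **11.5, 13.3, 13.5, 14.2 and 16.1.** Data are also requested on standard-of-care patients from 11.1.21 to 4.5.22, without consent. Study participants were consented from 4.6.22. The role of the earlier patients in the 10.7 test is not stated.

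**The concern.** A two-sample t-test or rank-sum test takes its standard error from two independent sets of people. If the treatment-phase change and the wait-phase change come from the same participants, the two means are correlated and that standard error is wrong.

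The likely source of the correlation is a shared score. If change restarts at the first visit, that visit's score ends one change and begins the other. If both changes start at intake, the intake score is in both. In the no-intervention group, the first score after intake is the one at the first visit. A wait-phase change that ends there and a treatment-phase change that restarts there must share it.

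This is the only test named in 10.7, and it carries Aim 2. At stake is whether its p-value means what the 0.05 threshold says it means.

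**Working it through.** **No plan figure to reproduce.** Section 10.7 has no power calculation, effect size, standard deviation or within-person correlation. The 200 in 11.2 is not derived. Inputs from the plan are alpha 0.05 and the two-sample test. My assumptions are a two-sided test, equal variances of the two changes, and every participant supplying both. The correlation between the changes is varied.

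**Formula.** Let two changes, each with variance V, come from the same n people with correlation r.

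- True SE² = 2V(1 − r)/n
- SE² used by the two-sample test = 2V/n
- True SE / used SE = √(1 − r)
- Actual two-sided alpha = 2 × [1 − Φ(1.96/√(1 − r))]

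The ratio does not depend on n.

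**Case (a): change restarts at the first visit.** Let A be the intake score, B the first-visit score and C the final score, each with variance 1. The changes are B − A and C − B.

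- *Exchangeable scores, correlation ρ.* Each change has variance 2(1 − ρ) and the covariance is −(1 − ρ), so r = −0.5 for any ρ. The ratio is √1.5 = 1.22. Alpha = 2 × [1 − Φ(1.60)] = 11.0%.
- *AR(1) scores, equally spaced.* The covariance is −(1 − ρ)², so r = −(1 − ρ)/2. For ρ = 0.5, r = −0.25 and alpha = 2 × [1 − Φ(1.753)] = 8.0%. For ρ = 0.7, r = −0.15 and alpha = 2 × [1 − Φ(1.828)] = 6.8%.

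**Case (b): both changes run from intake.** The changes are B − A and C − A.

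- *Exchangeable scores.* The covariance is +(1 − ρ), so r = +0.5. The ratio is √0.5 = 0.71. Alpha = 2 × [1 − Φ(2.772)] = 0.6%.
- *AR(1), ρ = 0.5.* The variances are 1 and 1.5 and the covariance is 0.75. The true variance of the difference is 1 + 1.5 − 1.5 = 1, against 2.5 used. The ratio is √0.4 = 0.63 and alpha is 0.2%.
- *Power, exchangeable.* Take an effect with 80% power under a paired test, that is 1.96 + 0.84 = 2.80 true SEs. The two-sample test rejects only beyond 1.96/0.707 = 2.77 true SEs. Power is Φ(2.80 − 2.77) = Φ(0.03), about 51%.

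**Range of r.** For r = −0.7, −0.3, 0, +0.3 and +0.7, actual alpha is 13.3%, 8.6%, 5.0%, 1.9% and 0.03%.

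**Incomplete overlap.** With n on each side and a fraction f of each side in common, r is replaced by f × r. For f = 0.5 and r = −0.5 the effective value is −0.25 and alpha is 8.0%. For f = 0.5 and r = +0.5 it is +0.25 and alpha is 2.4%.

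**Simulation check** (20,000 trials, n = 100 and n = 200):

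- Case (a), exchangeable: two-sample rejection 10.7-11.5%.
- Case (a), AR(1) with ρ = 0.7: 6.6-6.7%.
- Case (b), exchangeable: 0.5-0.6%.
- Paired test in all of these: 4.9-5.1%.

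**Separate cohorts.** Here r = 0, the ratio is 1 and alpha is 5%. The two-sample standard error is then valid.

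**The case against.** The strongest reply is that 10.7 never says the two sides are the same people. A reader might infer from 10.5 and 19.1 that they certainly are, and that the p-value is wrong whatever is done. The documents do not support that.

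- **Concurrent patients.** The rationale in 10.4 and 10.5 sets telemedicine patients against untreated referrals over the same period. Nobody can be both at once. This stands as a real alternative, although both sections then propose randomising wait-list individuals only.
- **The 11.1.21-4.5.22 patients.** They are not the consented participants and could in principle form an independent group. Against this, 13.5 and 14.2 call their data baseline, and the window closes before consent begins. It also spans only about 5 months, against a stated 3-4 month wait for a physician, so it would hold little treatment-phase follow-up. Their role remains unstated.
- **Section 11.3.** The absence of a telemedicine line proves little, because the minimal-intervention arm is missing too.
- **One change per person.** Taken literally, 10.7 defines a single initial-to-final change, so nobody need enter both sides. But a no-intervention participant has no second score before the first visit. On that reading it is unclear what these participants would contribute to the wait-list side.
- **Direction and size.** A reader might also take 11% as the expected error. It needs exchangeable scores, a shared first-visit score and complete overlap. Section 10.7 itself expects few records per patient, and 10.5 reports engagement of 33 to 74%. Where a minimal-intervention participant's wait phase ends at a monthly score before the visit, no score is shared, and under exchangeable scores r is zero. The sign depends on a baseline that the plan does not define.

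These points make the finding conditional. They do not remove it: the plan assigns no separate cohort to this test, and the trend statement in 10.7 is not a within-person analysis.

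**Conclusion.** The point holds conditionally. Section 10.7 leaves the telemedicine group undefined, and the sections that describe how the study runs best support its being the enrolled participants after their first visit. On that reading the two-sample test does not match the data. Under the equal-variance, complete-overlap scenarios, actual type I error is about 7-11% if change restarts at the first visit. It is about 0.6% or less if both changes run from intake, where 80% paired power falls to about 51% under exchangeable scores. Partial overlap brings both figures nearer to 5%. All correlations are assumptions, since the documents give none.

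Neither that the test is invalid on every reading, nor that it is always anti-conservative, can be concluded. With a separate cohort its standard error is correct. The two-sample test also suits the randomised Aim 1 contrast, although 10.7 does not assign it there.

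**What to change.** In 10.7:

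1. State who forms the telemedicine group, and what part, if any, the 11.1.21-4.5.22 patients play in the test.
2. Define the baseline and end score for the wait phase and for the treatment phase.
3. Where the same participants supply both phases, replace the two-sample test for Aim 2 with a within-person analysis. The simple form is a paired test on each person's wait-phase and treatment-phase change, expressed per month because waits differ. The alternative is a mixed model with participant random effects, which also uses people with incomplete records. With few scores per person, a simple covariance structure is safer than an unstructured one.
4. Assign the two-sample test to the randomised no-intervention versus minimal-intervention contrast (Aim 1).
5. Say that pairing corrects the standard error only. Treatment always follows waiting in this before-after comparison, so it remains confounded with time.

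The cost is about one paragraph, with no new patients or measurements. It should be settled before the Aim 2 data are analysed. No corrected sample size can be given, because the documents state no effect size, standard deviation or correlation.
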